2.1.1 Year 1 (Placebo-Controlled Portion of the Study)

Prior to the first dose in Year 1, all subjects in the study will be randomized into 4 arms, to receive 13 doses of BIIB054 (250, 1250, or 3500 mg) or placebo.

Subjects will be enrolled into 2 cohorts. Cohort A will be randomized first, in a 1:1:1:1 ratio into each of the 4 treatment arm and will include approximately 24 subjects. Randomization and dosing for Cohort B (approximately 287 planned subjects) will start after all subjects in Cohort A complete Week 12 assessments, and all available safety and PK data are reviewed by the IDMC. Randomization of subjects in Cohort B will be stratified by baseline (Day 1) MDS-UPDRS Part I + II + III total scores (≤ 35 and > 35) and striatum SBR (≤ 1.2 and > 1.2), and subjects will be randomized at Day 1 into 1 of 4 parallel dosing arms in each stratum. After all subjects in Cohort A complete Week 12 assessments (28 days after their third infusion), and before dosing any subjects in Cohort B, all available safety and PK data will be reviewed by the IDMC. No subjects in Cohort B may be dosed until the IDMC review is complete. The study schematic is presented in [Figure 1](#). After IDMC review is complete, subjects in Cohort B will be randomized, and dosing may begin. During the review period, subjects in Cohort A will continue to be dosed on a schedule of once every 4 weeks.

The first IDMC meeting will occur after the last subject in Cohort A completes Week 12 assessments, or approximately 6 months after the first subject has been enrolled in Cohort A, whichever comes first. Regular IDMC meetings will occur approximately every 3 months after the first meeting.

[REDACTED]

The Week 48 infusion is the last infusion of the placebo-controlled period, and Week 52 is the first dosing of the Dose-blinded portion of the study.

Any changes will be documented in a protocol amendment.

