4.1.2 Analyses period

Depending on the purpose, different analyses will be conducted on the following study periods:

1. DBE period. Only data in the DBE period will be included in these analyses. For example, incidence table of adverse events in the DBE period.
2. Placebo-controlled and DBE period. All the data in the placebo-controlled and DBE periods will be included in these analyses. For example, mean plot of actual laboratory values in the placebo-controlled and DBE period.

CONFIDENTIAL

The information contained herein may not be used, disclosed, or published without the written consent of Biogen MA Inc.

	Statistical Analysis Plan Dose Blinded Extension Period	V2.0
---	--	-------------

3. Active treatment (placebo-controlled and DBE) period (i.e., Total BIIB054 experience) period. Active treatment period is defined as the study period(s) that a subject is assigned to BIIB054. For early start subjects – subjects who are assigned to BIIB054 in both placebo-controlled and DBE period, all the data (placebo-controlled and DBE periods) will be included in the analyses. For delayed start subjects – subjects who are assigned to placebo in Year 1 and BIIB054 in the DBE period, only data in the DBE period will be included. For example, incidence table of adverse events in the active treatment (placebo-controlled and DBE) period will not include the AEs started on placebo treatment in year 1.

Subjects to be included in a certain output is determined by both the analysis population and the analysis period. For example, the incidence table of adverse events in the DBE period will include subjects in the safety population for the DBE period, i.e., all randomized subjects who received at least one dose of study treatment in the DBE period. The incidence table of adverse events in the active treatment (placebo-controlled and DBE) period will include subjects in the safety population for the active treatment period, i.e., all randomized subjects who received at least one dose of study treatment in the active treatment period. In this SAP we do not separately define the analysis population in each analysis period.

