4.5.2.2 **Incidence and incidence rate analysis for active treatment (placebo-controlled and DBE) period**

Due to the different length of active treatment (placebo-controlled and DBE) period in early start versus delayed start subjects, both incidence (proportion) tables and incidence rate tables will be used for AE analyses in this period. The entire follow-up time is from the first dose in

CONFIDENTIAL

The information contained herein may not be used, disclosed, or published without the written consent of Biogen MA Inc.

	Statistical Analysis Plan Dose Blinded Extension Period	V2.0
---	--	-------------

active treatment period (first dose in placebo-controlled period for early start subjects and first dose in DBE period for delayed start subjects) until the last day in the study.

The following incidence (proportion) will be provided for the active treatment (placebo-controlled and DBE) period. The follow-up adjusted incidence rate table will be provided for 1, 10, 12, 14, 16 and 17.

1. AEs by system organ class and preferred term sorted by decreasing frequency
2. AEs by system organ class and preferred term sorted by alphabetical order analysis
3. AEs by system organ class
4. AEs by preferred term
5. AEs with an incidence of 5% or more in any treatment group by preferred term
6. Severe AEs by system organ class and preferred term
7. Severe AEs by preferred term
8. AEs by maximum severity by system organ class and preferred term (System organ class will be presented alphabetically. Preferred term will be presented in decreasing frequency order).
9. AEs by maximum severity by preferred term (Preferred term will be presented in decreasing frequency order)
10. Study drug related AEs by system organ class and preferred term
11. Radioligand related AEs by system organ class and preferred term
12. SAEs by system organ class and preferred term
13. SAEs by preferred term
14. Study drug related SAEs by system organ class and preferred term
15. Radioligand related SAEs by system organ class and preferred term
16. AEs that led to discontinuation of study treatment by system organ class and preferred term
17. AEs that led to withdrawal from study by system organ class and preferred term
18. AEs that occurred within 2 hours from infusion start by system organ class and preferred term

The following listings will be provided for the placebo-controlled and DBE period:

1. Listing of AEs
2. Listing of SAEs

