Potentially Clinically Significant (PCS) laboratory abnormalities analyses

Please refer to the placebo-controlled SAP for the parameters and criteria for potentially clinically significant laboratory abnormalities analyses.

The number of subjects with potentially clinically significant laboratory abnormalities post-baseline will be summarized for the active treatment (placebo-controlled and DBE) period.

CONFIDENTIAL

The information contained herein may not be used, disclosed, or published without the written consent of Biogen MA Inc.

	Statistical Analysis Plan Dose Blinded Extension Period	V2.0
---	--	-------------

Subjects need to have at least one post-baseline evaluation in the active treatment period in order to be included in the analysis. For early start subjects, the placebo-controlled baseline will be used and abnormalities that occurred in either placebo-controlled or DBE period will be included. For delayed start subjects, the DBE baseline will be used and PCS abnormalities that occurred in the DBE period based on DBE baseline will be included.

A listing of subjects with PCS laboratory abnormalities in the active treatment (placebo-controlled and DBE) period will also be provided, with all the data in the placebo-controlled and DBE period will be listed.

Potential serious hepatotoxicity

Potential serious hepatotoxicity is defined as ALT or AST > 3x ULN and total bilirubin > 2x ULN at any time post-baseline, not necessarily concurrent, in the active treatment (placebo-controlled and DBE) period. A scatterplot of the maximum post-baseline ALT or AST value relative to ULN and maximum post-baseline total bilirubin value relative to ULN (not necessarily concurrent) will be provided. In addition, a line plot of ALT, AST, ALP and total bilirubin values over time for each subject with potential serious hepatotoxicity will be provided.

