4.5.7 C-SSRS Data

The Columbia Suicide Severity Rating Scale (C-SSRS) is an assessment that evaluates suicidal ideation and behavior. There are 5 “Yes/No” questions on suicidal ideation following the increasing severity order: (1) Wish to be dead, (2) Non-specific active suicidal thoughts, (3) Active suicidal ideation with any methods (not plan) without intent to act, (4) Active suicidal ideation with some intent to act, without specific plan, (5) Active suicidal ideation with specific plan and intent, and 6 “Yes/No” questions on suicidal behavior

CONFIDENTIAL

The information contained herein may not be used, disclosed, or published without the written consent of Biogen MA Inc.

	Statistical Analysis Plan Dose Blinded Extension Period	V2.0
---	--	-------------

following the increasing severity order: (6) Preparatory acts or behavior, (7) Aborted attempt, (8) Interrupted attempt, (9) Actual attempt, (10) Suicidal behavior, (11) Suicide (only at post-baseline visits). Another “Yes/No” question of whether the subject has engaged in non-suicidal self-injurious behavior is also collected.

The summary table for C-SSRS will be conducted for the active treatment (placebo-controlled and DBE) period. Number of subjects who answered “Yes” to each of the 11 questions post-baseline, subjects who answered “Yes” to at least one question for suicidal ideation, subjects who answered “Yes” to at least one question for suicidal behavior, and subjects who have engaged in non-suicidal self-injurious behavior will be presented.

A listing of subjects with any suicidal ideation or behavior at baseline or post-baseline will be provided for the placebo-controlled and DBE period.

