4.5.8 MRI Safety Data

Brain MRI safety findings are assessed at Screening visit, Week 24, 52, 96, 148 and 4 weeks after last dose/ET visits.

The MRI safety result is classified as normal or abnormal. Shift table from normal or unknown MRI at baseline to abnormal post-baseline MRI will be summarized in the active treatment (placebo-controlled and DBE) period. The worst post-baseline record of each subject is selected. A listing of details for abnormal brain MRI findings will be presented for placebo-controlled and DBE period.

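### DBE SAP: the any-time safety tables for the active treatment period show early start beside delayed start as raw counts or percentages, although early start has a planned 52 more weeks on drug and two more scheduled MRI scans

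*SAP*

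**What the plan says.** All sections are in the DBE SAP (V2.0) unless stated.

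- **Period.** Section 4.1.2 defines the active treatment period. For early-start subjects "all the data (placebo-controlled and DBE periods) will be included in the analyses". For delayed-start subjects only extension data count. Section 2.1.1 fixes where the extension begins: "Week 52 is the first dosing of the Dose-blinded portion of the study".
- **Layout.** Section 4.1 puts delayed start, early start and BIIB054 total in one table for safety outputs.
- **AEs.** Section 4.5.2.2 gives the reason for using both proportions and rates: "Due to the different length of active treatment (placebo-controlled and DBE) period in early start versus delayed start subjects". It then limits the rates: "The follow-up adjusted incidence rate table will be provided for 1, 10, 12, 14, 16 and 17". Tables 6 and 7 (severe AEs) are not among these.
- **Laboratory.** Section 4.5.3.2: "The number of subjects with potentially clinically significant laboratory abnormalities post-baseline will be summarized for the active treatment" period. Shifts and abnormalities from either period count for early start; only those in the extension count for delayed start.
- **Vital signs and ECG.** Sections 4.5.4 and 4.5.5 summarise vital-sign abnormalities at any post-baseline visit, ECG shifts and QTcF outliers over the same period.
- **C-SSRS.** Section 4.5.7: "The summary table for C-SSRS will be conducted for the active treatment" period, as numbers of subjects.
- **MRI.** Section 4.5.8: "Brain MRI safety findings are assessed at Screening visit, Week 24, 52, 96, 148 and 4 weeks after last dose/ET visits". The shift table takes each subject's worst post-baseline record.
- **Extension-only version.** Section 4.5.1 assigns the extension-only period to AE analyses and to nothing else.

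**The concern.** A proportion of subjects ever abnormal rises with time observed and, for findings seen only on a scan, with the number of scans. The plan accepts this for AEs and gives the remedy for six tables. The same reasoning applies to the other any-time tables, which get neither a rate nor, apart from severe AEs, an equal-window version.

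These tables serve the secondary objective on dose-related safety. A higher early-start percentage could reflect cumulative toxicity or only longer observation, and the table alone cannot tell the two apart. It could also hide a higher early-exposure rate in delayed start. The BIIB054 total column pools two observation lengths.

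**Working it through.** **The plan's own safety figure.** Section 3 states an 80% chance of detecting an AE with a 1.6% rate and 90% for 2.3%, with 100 subjects per arm. 1 − (1 − 0.016)^100 = 0.801 and 1 − (1 − 0.023)^100 = 0.902, so both reproduce. They do not address length of observation, and the plan gives no event rates for the tables at issue. The annual risks below are therefore assumptions, starting from that 1.6%.

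**Time on drug.**
- Year 2 completers dose to Week 96 and have a Final Visit 12 weeks later (section 2.1.2): Week 108. Early start has 108 weeks, delayed start 108 − 52 = 56.
- Longest case: up to 16 further doses every 4 weeks, 96 + 16 × 4 = Week 160, plus an assumed 12 weeks = Week 172. Early start has 172 weeks, delayed start 120.

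**Expected proportions at equal hazard.** With annual risk p, λ = −ln(1 − p)/52 per week, and the expected proportion ever abnormal is 1 − exp(−λt). For p = 5%, λ = 0.000986. At Week 108 early start gives 1 − exp(−0.1065) = 10.1%, delayed start 1 − exp(−0.0552) = 5.4%, ratio 1.88.

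| Annual risk | Week 108, early vs delayed | Ratio | Week 172, early vs delayed | Ratio | Ratios with 10% Year 1 dropout (Week 108 / 172) |
|---|---|---|---|---|---|
| 1.6% | 3.3% vs 1.7% | 1.91 | 5.2% vs 3.7% | 1.42 | 1.77 / 1.30 |
| 5% | 10.1% vs 5.4% | 1.88 | 15.6% vs 11.2% | 1.40 | 1.74 / 1.28 |
| 10% | 19.7% vs 10.7% | 1.83 | 29.4% vs 21.6% | 1.36 | 1.70 / 1.25 |
| 20% | 37.1% vs 21.4% | 1.74 | 52.2% vs 40.2% | 1.30 | 1.61 / 1.19 |

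The last column uses the plan's 10% dropout at Week 52, assumed uniform over Year 1. Early-start dropouts stay in the denominator; placebo subjects who leave in Year 1 never enter the active period. Mean early-start follow-up becomes 0.9 × 108 + 0.1 × 26 = 99.8 weeks (excess 43.8) or 0.9 × 172 + 0.1 × 26 = 157.4 weeks (excess 37.4).

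**MRI.** Early start has scheduled on-drug scans at Weeks 24, 52, 96 and 148. Delayed start has Weeks 96 and 148, because a Week 52 scan before the first extension dose is its baseline (section 4.1). Both groups also have the scan after last dose. With an assumed independent 5% chance per scan, the worst-record proportion is 1 − 0.95^k:
- 4 vs 2 scans (to Week 148 without the last-dose scan, or to Week 96 with it): 18.5% vs 9.8%, ratio 1.90.
- 5 vs 3 scans (to Week 148 with it): 22.6% vs 14.3%, ratio 1.59.

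**Does a rate remove the gap?** A rate censored at first event has expectation λ in both groups: at 5%, about 5.15 per 100 subject-years, ratio 1.00. The incidence rate defined in section 4.5.1 divides subjects with an event by their whole follow-up. At Week 108 its ratio would be 1.88 × 56/108 = 0.97 at 5% annual risk and 1.74 × 56/108 = 0.90 at 20%. It removes most of the gap and slightly over-corrects.

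**The case against.** Several points on the other side stand and set the limits of this one.

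- A reader might infer that severe AEs have no fair comparison. They do: section 4.5.2.1 lists severe-AE tables 3 and 4 for the DBE period, defined in section 4.1.2 by "Only data in the DBE period will be included". Only the active-treatment tables 6 and 7 are affected.
- A reader might infer that all laboratory, vital-sign and ECG output is affected. The by-visit summaries in sections 4.5.3.1, 4.5.4 and 4.5.5 are not any-time proportions and do not have this fault. Nor can they replace the outlier tables.
- A reader might infer that early start must look worse in every table. The excess is an expectation at equal constant hazard. Delayed-start subjects enter the active period a year later with a new baseline, and counts of rare events are noisy.
- A ratio near 2.1 arises at Week 96 (96 vs 44 weeks, 10% annual risk), but the plan names no Week 96 safety analysis. Section 4.10 places the comprehensive safety profile at end of study.
- A reader might also infer poorer MRI detection per scan period in delayed start. Over the first 44 weeks on drug each group has one scheduled post-baseline scan (Week 24 for early start, Week 96 for delayed start). The difference lies in total scan count. A lasting finding would also be caught by a later scan.
- No test or formal early-versus-delayed safety comparison is planned. Section 4.2.5 tabulates weeks on treatment, and the Year 1 SAP (sections 5.4.3 to 5.4.8) covers the same outcomes against placebo over a common planned year.
- Laboratory and MRI abnormalities are dated only by the visit that finds them, so a first-event rate is approximate.

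The C-SSRS summary in section 5 for data after 7 March 2020 uses a calendar cut, so it does not equalise time on drug. None of these points supplies a rate or an equal-window version for the non-AE any-time tables.

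**Conclusion.** The point holds for the active-treatment laboratory shift and PCS tables, vital-sign abnormalities, ECG shifts and QTcF outliers, C-SSRS, the MRI worst-record shift, and severe-AE tables 6 and 7. Followed as written, the plan gives early-start and delayed-start proportions confounded with length of observation and, for MRI, with scan count.

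At equal constant hazard the expected ratio is about 1.7 to 1.9 at Week 108 and 1.3 to 1.4 at Week 172, or about 1.6 to 1.8 and 1.2 to 1.3 after 10% Year 1 dropout. These figures rest on assumed annual risks of 1.6% to 20%. The MRI ratios rest on an assumed, independent per-scan risk. This is a defect of descriptive presentation: no planned inference is biased, and the documents do not support a claim that the observed difference must run one way. It is worth correcting because the plan already states the reason and defines the method.

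**What to change.** Keep every raw table and add the following.

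- **Severe-AE tables 6 and 7, and the any-time laboratory, vital-sign, ECG and C-SSRS tables (sections 4.5.2.2, 4.5.3.2, 4.5.4, 4.5.5, 4.5.7).** Add either a rate per 100 subject-years using the section 4.5.1 follow-up definition, preferably censored at first event, or a proportion over a common window from first BIIB054 infusion in both groups. The first 44 weeks would serve, since Week 52 to Week 96 is 44 weeks.
- **MRI (section 4.5.8).** Next to the worst-record table, report abnormal shifts per scan by weeks since first BIIB054 infusion, with the number of scans shown. A person-time rate alone would not deal with unequal scan counts.

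The cost is SAP wording and a few extra tables from data already collected. The common-window version leaves out later events, which the raw table still shows.

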4.5.4 Vital Sign Data

For vital sign data analyses, the analysis period is active treatment (placebo-controlled and DBE) period. Vital sign parameters include body temperature, systolic blood pressure, diastolic blood pressure, heart rate, respiration rate and weight. Vital signs will be measured with the subject supine and after the subject has been resting for at least 10 minutes. The descriptive statistics for actual values will be summarized at each visit in the active treatment (placebo-controlled and DBE) period. Plot of mean vital sign values in the active treatment (placebo-controlled and DBE period) may be provided.

Summary of change from baseline including number of evaluable subjects, mean, standard deviation, median, 25% and 75% quartiles, minimum, and maximum values will be summarized at each visit in the active treatment (placebo-controlled and DBE) period. Placebo-controlled baseline will be used for early start subjects and DBE baseline will be used for delayed start analysis.

The analysis of vital signs will also focus on the incidence of clinically relevant abnormalities at any post-baseline visit in the active treatment (placebo-controlled and DBE) period. Please refer to the placebo-controlled SAP for the criteria to assess potential clinically relevant abnormalities in vital sign. The incidence and percentage of clinically relevant abnormalities

CONFIDENTIAL

The information contained herein may not be used, disclosed, or published without the written consent of Biogen MA Inc.

	Statistical Analysis Plan Dose Blinded Extension Period	V2.0
---	--	-------------

determined by each criterion will be summarized in the active treatment (placebo-controlled and DBE) period.

A listing of subjects with clinically relevant abnormalities at any post-baseline visit in the active treatment (placebo-controlled and DBE) period will also be provided. All the data in the placebo-controlled and DBE period will be listed.

Visit windows for by visit summaries

For vital sign by visit summaries, the analysis visit should be defined using windows (see Table 2 in the Appendix). For the same parameter for a subject, if there is more than 1 record in the same analysis visit window, then select the record closest to the target visit day. If there are 2 records in the same analysis visit window with the same distance from the target visit day, then select the record with the later date.

4.5.5 ECG Data

For ECG data analyses, the analysis period is active treatment (placebo-controlled and DBE) period. The descriptive statistics for actual values will be summarized at each visit in the active treatment (placebo-controlled and DBE) period. Plot of mean ECG values in the active treatment (placebo-controlled and DBE) period may be provided.

Shift from normal or unknown ECG at baseline to abnormal post-baseline ECG, will be summarized in the active treatment (placebo-controlled and DBE) group. The number of subjects with potential QTcF interval outlier post-baseline will also be summarized in the active treatment (placebo-controlled and DBE) period. The criteria of defining QTcF interval outliers is specified in the placebo-controlled SAP. For early start subjects, the placebo-controlled baseline will be used. For delayed start subjects, the DBE baseline will be used.

A listing of subjects with abnormal ECG status post-baseline in the active treatment (placebo-controlled and DBE) period will be provided. All data in the placebo-controlled and DBE period will be listed.

4.5.6 Physical and Neurological Examination

Abnormal findings during physical and neurological examinations are captured as adverse events and will be reflected in the summary of AEs.

4.5.7 C-SSRS Data

The Columbia Suicide Severity Rating Scale (C-SSRS) is an assessment that evaluates suicidal ideation and behavior. There are 5 “Yes/No” questions on suicidal ideation following the increasing severity order: (1) Wish to be dead, (2) Non-specific active suicidal thoughts, (3) Active suicidal ideation with any methods (not plan) without intent to act, (4) Active suicidal ideation with some intent to act, without specific plan, (5) Active suicidal ideation with specific plan and intent, and 6 “Yes/No” questions on suicidal behavior

CONFIDENTIAL

The information contained herein may not be used, disclosed, or published without the written consent of Biogen MA Inc.

	Statistical Analysis Plan Dose Blinded Extension Period	V2.0
---	--	-------------

following the increasing severity order: (6) Preparatory acts or behavior, (7) Aborted attempt, (8) Interrupted attempt, (9) Actual attempt, (10) Suicidal behavior, (11) Suicide (only at post-baseline visits). Another “Yes/No” question of whether the subject has engaged in non-suicidal self-injurious behavior is also collected.

The summary table for C-SSRS will be conducted for the active treatment (placebo-controlled and DBE) period. Number of subjects who answered “Yes” to each of the 11 questions post-baseline, subjects who answered “Yes” to at least one question for suicidal ideation, subjects who answered “Yes” to at least one question for suicidal behavior, and subjects who have engaged in non-suicidal self-injurious behavior will be presented.

A listing of subjects with any suicidal ideation or behavior at baseline or post-baseline will be provided for the placebo-controlled and DBE period.

